### **Methods and analysis**

This will be a prospective, observational study that includes patients undergoing elective cardiovascular surgery with cardiopulmonary bypass (CPB). Microcirculation will be quantified with sublingual incident dark field videomicroscopy. Mitochondrial respiration will be measured by performing a substrate-uncoupler-inhibitor titration protocol with high resolution respirometry on peripheral blood mononuclear cells at baseline and serial timepoints during resuscitation and at recovery as a possible liquid biomarker. Plasma samples will be preserved for future analysis to examine endothelial injury and other mechanisms of microcirculatory dysfunction. Thirty-day ventilator and vasopressor-free days (VVFDs) will be measured as a primary outcome, along with sequential organ failure assessment scores, and other clinical parameters to determine if changes in microcirculation and mitochondrial respiration are more strongly associated with clinical outcomes compared to traditional resuscitation targets.

This will be the first prospective study to examine both microcirculatory and mitochondrial function in human patients with circulatory shock undergoing cardiac bypass and address a key mechanistic knowledge gap in the cardiovascular literature. The results of this study will direct future research efforts and therapeutic development for patients with shock.

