## **Timeline and techniques for data collection**

Data for each subject will be collected at time points outlined in **Error! Reference source not found.** Prior to surgery, baseline biologic samples, microcirculation imaging, and clinical data will be obtained. Repeated measurements will be obtained in the ICU and surgical floor. Long-term clinical outcomes will be recorded at 30-days or upon discharge.

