### **Fig 1. Timeline of data collection.**

## **Demographic and resuscitation data**

Demographic values including age, gender, and ethnicity will be recorded. Preoperative risk scores including the STS (Society of Thoracic Surgeons) mortality score and euroSCORE II (European System for Cardiac Operative Risk Evaluation) will be calculated [51,52]. Intraoperative data including cardiopulmonary bypass time, cross clamp time, blood product use, intravenous fluid administration, and vasoactive administration will be recorded. ICU clinical data (hemodynamics, laboratory testing, etc.), resuscitation data (intravenous fluids, vasoactive administration, blood transfusion, etc.), and clinical outcomes (VVFDs, ICU length of stay, hospital LOS, etc.) will be recorded as indicated in **Error! Reference source not found.** Sequential organ failure assessment (SOFA) scores will be calculated prior to surgery (baseline), as well as 24 and 72 hours after surgery.

[figure not shown]

[figure not shown]
Figure 1

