### Outcome measures

Our hypothesis is that patients with poor post-operative sublingual functional capillary density (defined as a PVD < 22 mm/mm^2 and MHI > 0.4) will have a higher degree of postoperative cardiovascular and pulmonary organ injury compared to patients with normal postoperative microcirculation. The primary outcome for this study will be VVFDs during the first 30 days after surgery. This outcome was chosen because our elective cardiac surgery patients are managed using early recovery after surgery (ERAS) protocols, with a goal to be extubated and weaned off vasopressors within 24 hours after surgery [21,22]. VVFDs will be calculated as a reverse count of consecutive days without requiring ICU-level respiratory or vasopressor support (**Error! Reference source not found.**). Our research group has used a similar primary outcome in a previous clinical trial [23]. The day of operation (day zero) will not be included as all patients undergoing cardiovascular surgery with CPB require mechanical ventilation and vasoactive medications on the day of surgery. Ventilator days will include mechanical ventilation via endotracheal tube or tracheostomy, high-flow nasal cannula  $\geq$  40 liters/minute with an FiO2 > 40%, or non-invasive positive pressure ventilation not prescribed at home. Non-invasive positive pressure ventilation and HFNC will be included as these both require the patient to remain in our ICU. Vasoactives include epinephrine, norepinephrine, vasopressin, phenylephrine, dobutamine, or milrinone at any dose. Subjects in need of respiratory or vasopressor support on day 30, or die before day 30 will be assigned zero VVFDs. If the patient is discharged prior to hospital day 30 a “last status carried forward” approach will be used. Secondary outcomes will include sequential organ failure assessment (SOFA) score on day 1, day 3, diagnosis of acute kidney injury (defined as an increase in serum creatinine  $\geq$  0.3 mg/dL within 2 days), and hospital length of stay.

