### Data sources

This study will in no way alter or interfere with the clinical care of any shock or control subject as determined by the medical care team. All clinical data will be abstracted from the paper or electronic (EPIC and Sunrise) medical record. To assist in this effort, we will perform manual review of the medical record for each study patient. At HUP, each data collector and the Data Coordinator have completed extensive initial training and monitor data quality quarterly, including inter-rater reliability.

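### VVFD carry-forward is triggered by discharge, not by unknown status, and no day-30 check is dated, so an undetected post-discharge death or readmission on support would be over-scored

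*Combined protocol and SAP*

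**What the plan says.** The abstract sets the horizon: "Thirty-day ventilator and vasopressor-free days (VVFDs) will be measured as a primary outcome". The Outcome measures section then gives three scoring rules.

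- Counting rule: "VVFDs will be calculated as a reverse count of consecutive days without requiring ICU-level respiratory or vasopressor support". Day 0 is excluded, so the maximum is 30.
- Zero rule: "Subjects in need of respiratory or vasopressor support on day 30, or die before day 30 will be assigned zero VVFDs".
- Carry-forward: if the patient is "discharged prior to hospital day 30 a “last status carried forward” approach will be used".

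On timing, the section Timeline and techniques for data collection states: "Long-term clinical outcomes will be recorded at 30-days or upon discharge". Demographic and resuscitation data adds that "clinical outcomes (VVFDs, ICU length of stay, hospital LOS, etc.) will be recorded as indicated in" a figure, which is not shown. Study design and setting describes repeated measures from baseline to 30 days after surgery. Data sources states: "All clinical data will be abstracted from the paper or electronic (EPIC and Sunrise) medical record", with manual review for each patient but no date for that review.

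**The concern.** The trigger for carry-forward is discharge itself. Carrying the last status forward is a reasonable convention when nobody knows what happened. Here it also applies where the medical record, which is the plan's own data source, could show what happened. Because outcomes may be recorded on discharge, a team could close the record that day and comply with the text. A later death, or a readmission on ventilatory or vasoactive support, would then go unseen, and the subject would be scored as though discharge status had lasted to day 30.

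This is probably the usual scoring route. Patients are elective and managed "with a goal to be extubated and weaned off vasopressors within 24 hours after surgery", so most are likely to leave hospital well before day 30. That is an inference, since no expected length of stay is given. A missed event moves a subject from the bottom or middle of the scale to near the top. It can also put the subject in the wrong class in the ROC and Youden analysis of prolonged VVFDs.

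**Working it through.** **1. The rules together.** The zero rule is not limited to in-hospital events, and the reverse count runs over 30 days. A known death before day 30 should therefore score 0, and known support after discharge should restart the count. Carry-forward has no stated exception and no stated rank against these rules. What remains exposed is the event that nobody looked for.

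**2. Score of a subject with a missed event.** Carried-forward score = 30 − last in-hospital support day. Last support on day 0, 1, 3 or 5 (assumed) gives 30, 29, 27 or 25. The defined score is 0 for a death before day 30, and at most 30 − 15 = 15 if support was needed on day 15.

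**3. Share of days filled by carry-forward.** For an assumed discharge on day 5 to 10, carry-forward supplies 30 − 5 = 25 to 30 − 10 = 20 of the 30 days (83% to 67%). These days are wrong only if an event occurred.

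**4. The plan's sample size.** Sample size and power gives 134 evaluable subjects, 1:1 (134/2 = 67 per group), a 2-day difference, one-sided α = 0.05, and 0.8 (printed as β, read here as power). No SD is visible, so 134 cannot be reproduced independently. Solving backwards:

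- Normal approximation: SD = 2/(1.645 + 0.842) × √(67/2) = 4.66.
- Noncentral t: SD = 4.63, used below as an assumption.

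**5. Shift in a group mean from one missed event.**

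| Last in-hospital support day | Missed death | Missed day-15 readmission (at least) |
|---|---|---|
| 0 | 30/67 = 0.45 | (30 − 15)/67 = 0.22 |
| 1 | 29/67 = 0.43 | (29 − 15)/67 = 0.21 |
| 5 | 25/67 = 0.37 | (25 − 15)/67 = 0.15 |

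For last support on day 1, a missed death is 0.43/2 = 22% of the target difference.

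**6. Power, both directions.** One subject is rescored from 0 to 29 in one group, with no offset in the other. For true mean m, the new mean is m′ = m + 29/67 and the new variance is (66 × 4.63² + 67m² + 29² − 67m′²)/66. Power uses the pooled SD.

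| Miss in | Difference | Assumed true mean | SD after rescoring | Pooled SD | Power |
|---|---|---|---|---|---|
| none | 2.00 | – | – | 4.63 | 0.80 |
| low PVD | 2 − 0.43 = 1.57 | 24 | 3.59 | 4.15 | 0.70 |
| low PVD | 1.57 | 27 | 3.21 | 3.98 | 0.73 |
| high PVD | 2 + 0.43 = 2.43 | 26 | 3.34 | 4.04 | 0.97 |
| high PVD | 2.43 | 29 | 2.92 | 3.87 | 0.98 |

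The means stop there because of the ceiling. On a 0–30 scale the variance at mean m cannot exceed about m(30 − m), and 4.63² = 21.4 requires m of about 29.3 or less. The low-PVD mean, 2 days lower, can then be at most about 27.3.

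**7. ROC analysis.** No VVFD cutoff for a poor outcome is stated. If poor means VVFD below c, then 0 scored as 29 is misclassified for every c from 1 to 29, and 15 scored as 29 for every c from 16 to 29.

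**The case against.** The strongest reply is that the plan already has a 30-day horizon. The design section runs measures to 30 days, the zero rule covers any death before day 30, and each patient's record is reviewed by hand. The timing sentence can also be read distributively, with VVFDs at 30 days and length of stay at discharge. In addition, Fig 1 (timeline), Fig 3 (VVFD scenarios) and the S1 Appendix are not shown, and Fig 3 is the natural place for a readmission or a post-discharge death.

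Much of this stands. It shows what the authors probably intended, and it rules out one stronger reading that a reader might infer: that the plan scores every post-discharge death or readmission near the maximum. The zero rule and the reverse count sit in the same paragraph as carry-forward and are best read as governing any event that becomes known. The reply does not supply a date for the review or an order among the rules, and a review done at discharge cannot see later events.

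A second reading to resist is that the study will lose power or be biased toward no difference. The documents give no post-discharge event rate, length of stay or split by PVD group, and one miss in the high-PVD group works the other way. The SD is back-solved, and if the pilot data were scored by the same rule it may already reflect such misses. One event would also barely move a median, which the plan reports when data are not normally distributed.

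**Conclusion.** The point holds for undetected events, on the visible text. A rule triggered by discharge, together with permission to record outcomes at discharge, lets the primary outcome be scored without anyone looking at day 30. The effect per event is firm arithmetic once the last support day is assumed: 0.43 day for a missed death and at least 0.21 day for a missed day-15 readmission, with last support on day 1 and 67 per group. The power figures (about 0.70 to 0.73 for one low-PVD miss, about 0.97 for one high-PVD miss) are illustrations that also rest on an SD of 4.63 and assumed group means. The number of events and their split are unknown, so neither a net bias nor its direction is claimed. This is a cheap improvement to the scoring of the primary outcome, and it reduces to an edit of the text if the figures already contain the rule.

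**What to change.** In Timeline and techniques for data collection, replace the choice of 30 days or discharge, for VVFDs, with a medical-record review at or after day 30 for every subject. It should record vital status and any readmission on ventilatory or vasoactive support. For subjects already enrolled, do it retrospectively.

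In Outcome measures, state that:

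1. the zero rule and the reverse count take precedence over carry-forward for any event found through day 30, before or after discharge;
2. carry-forward is used only when the review leaves day-30 status unknown;
3. the number of such subjects is reported by PVD group, with a note that events outside the record may still be missed.

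If Figs 1 and 3 already show this, put the rule in the text and repair the cross-references.

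The cost is at most 140 chart checks by the existing data collectors, in the record already named as the data source, plus the wording changes in two sections.

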## **Sample size and power**

Using data from our previous foundational work as well as unpublished pilot data, we anticipate a 1:1 allocation of patients to the high ( $PVD > 22\text{mm/mm}^2$ ) and low group ( $PVD \leq 22\text{ mm/mm}^2$ ). We will need a sample size of at least 134 subjects to detect at least a 2-day difference in ventilator and vasopressor-free days (VVFDs) with a  $\beta=0.8$ , using a one-sided t-test  $\alpha=0.05$  [5,6]. We will enroll a total of 140 subjects to allow for a 5% loss to follow-up (surgical delay, ICU delay, cancelled surgery, etc.) and exclusion due inadequate microcirculation video quality (S1 Appendix).

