## **Inclusion criteria**

Adult patients ( $\geq 18$  years old) receiving elective CABG or valvular surgery requiring cardiopulmonary bypass are eligible for enrollment. Post-operative patients with circulatory shock will be identified by having:

1. Either vasopressor-dependent hypotension or low cardiac output requiring inotropic support
2. Signs of end-organ injury or impaired tissue perfusion defined by one of the following criteria:
  - a. Normothermic patients with a capillary refill time  $> 3$  seconds
  - b. Serum lactate  $> 2$  mmol/dL
  - c. Mixed venous oxygen saturation ( $SvO_2$ )  $< 60\%$

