## **Exclusion criteria**

Patients will be excluded if they are unable to tolerate sublingual microcirculatory flow imaging (e.g., non-intubated patients dependent upon oxygen by facemask, poor mouth opening), receiving an emergent procedure, have an active malignancy, or mitochondrial disorder.

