### Statistical and analysis plans

Continuous variables characterizing demographical data, microcirculation data, and mitochondrial respiration measurements, and outcomes data will be reported as means with standard deviations if normally distributed or medians with interquartile ranges if not normally distributed. Categorical variables will be represented as frequencies and proportions. To examine the predictive performance of selected variables for the primary outcome, we will construct receiver operator characteristic curves for threshold values of PVD, MHI, lactate,  $SvO_2$ , mean arterial pressure, and cardiac index. A Youden index will be calculated to determine the best cutoff value for determining prolonged VVFDs.

Linear regression modeling will be used to examine the relationship between L/P ratio and postoperative microcirculation variables. We will perform univariate analyses on candidate predictor variables of L/P ratio including PVD, MHI, LFTs, creatinine, CPB time, cross clamp time, and catecholamine administration. Multiple linear regression analysis will be used to model the effect of significant predictors. Repeated measure ANOVA will be used to compare changes in microcirculatory variables, mitochondrial respiration, and mitochondrial reactive oxygen species production over time. To adjust for multiple comparisons, post-hoc pairwise Tukey Kramer t-tests will be performed. All analyses will use statistical software (SAS version 15.1, Cary, NC; Prism v 9.0, Graph-Pad Software, San Diego, CA).

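### The creatinine-only AKI definition can score maintenance-dialysis patients as new AKI and can miss cases treated early with renal replacement (minor, cheap to fix)

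*Combined protocol and SAP*

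**What the plan says.** All references are to the combined protocol and SAP.

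- **Outcome measures.** The secondary outcomes include "diagnosis of acute kidney injury (defined as an increase in serum creatinine" of at least "0.3 mg/dL within 2 days), and hospital length of stay". No baseline creatinine is named and no start is given for the 2 days.
- **Inclusion criteria.** Adults "receiving elective CABG or valvular surgery requiring cardiopulmonary bypass are eligible for enrollment".
- **Exclusion criteria.** "Patients will be excluded if they are unable to tolerate sublingual microcirculatory flow imaging", or if they are "receiving an emergent procedure, have an active malignancy, or mitochondrial disorder". Neither section has a renal criterion.
- **Statistical and analysis plans.** Creatinine appears only among "candidate predictor variables of L/P ratio including PVD, MHI, LFTs, creatinine, CPB time, cross clamp time, and catecholamine administration". No analysis set and no between-group test is given for AKI; categorical variables are to be summarised as counts and proportions.
- **Sample size and power.** "We will need a sample size of at least 134 subjects to detect at least a 2-day difference" in VVFDs, with 140 to be enrolled, and "we anticipate a 1:1 allocation of patients to the high" and low PVD groups.

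The supplied text does not mention dialysis, renal replacement or urine output.

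**The concern.** An event definition needs a population that can have the event. A patient without native kidney clearance accumulates creatinine between dialysis sessions. A rise of 0.3 mg/dL there says nothing about new injury, yet it satisfies the definition.

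The opposite error is also possible. Renal replacement lowers creatinine, and starting it is not a criterion. A severe case treated before a qualifying rise is recorded can therefore be scored as no AKI.

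The same section already separates old from new support for another organ. Non-invasive ventilation counts towards ventilator days only if the patient was not already using it at home. The kidney outcome has no matching rule.

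At stake is the AKI rate and any comparison of it between PVD groups. Those groups are not randomised, so pre-existing dialysis need not be balanced between them.

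**Working it through.** The plan states no figure on this point, so there is none to reproduce. The check has two parts.

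**1. Applying the definition literally**

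| Patient | Result under the stated rule | Correct as new AKI? |
|---|---|---|
| Maintenance dialysis, rise of at least 0.3 mg/dL between sessions | AKI | No |
| New renal replacement after a qualifying rise within 2 days | AKI | Yes |
| New renal replacement before a qualifying rise is recorded | Not AKI | No, missed |

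The first and third rows are wrong classifications produced by the rule itself.

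**2. Size of the false-positive error (illustration)**

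From the documents: 140 enrolled and an expected 1:1 split, so 140/2 = 70 per PVD group.

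Assumed, because the documents give no figure:
- prevalence of maintenance dialysis q = 1%, 3% or 5%
- proportion of dialysis patients meeting the rule f = 100% (worst case) or 50%
- AKI rate in all other subjects p = 25%
- all k dialysis patients fall in one PVD group

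Number on dialysis: 140 × 0.01 = 1.4, 140 × 0.03 = 4.2, 140 × 0.05 = 7, taken as k = 1, 4 and 7.

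Observed rate in that group = [k·f + p(70 − k)]/70. With the k subjects removed it is p. The overstatement is therefore k(f − p)/70.

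| k | Observed rate, f = 100% | Overstatement, f = 100% | Overstatement, f = 50% |
|---|---|---|---|
| 1 | (1 + 17.25)/70 = 26.1% | 0.75/70 = 1.1 points | 0.25/70 = 0.4 points |
| 4 | (4 + 16.5)/70 = 29.3% | 3/70 = 4.3 points | 1/70 = 1.4 points |
| 7 | (7 + 15.75)/70 = 32.5% | 5.25/70 = 7.5 points | 1.75/70 = 2.5 points |

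Even split, for example k = 4 with two per group and f = 100%: each group reads (2 + 0.25 × 68)/70 = 27.1%, so both rise by 2.1 points and the difference between them is unchanged at zero. If the true rates differ by D, the observed difference is D × 68/70 = 0.97D, a slight dilution.

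Share of all counted AKI events that are false = qf/[qf + (1 − q)p], which does not depend on the number enrolled:
- low end (q = 1%, f = 50%, p = 30%): 0.005/(0.005 + 0.297) = 1.7%
- high end (q = 5%, f = 100%, p = 20%): 0.05/(0.05 + 0.19) = 20.8%

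The number of missed cases cannot be estimated. The documents give no rate of early renal replacement.

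**The case against.** The case for leaving the definition alone has several parts.

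- **Eligibility is inferred from silence.** A reader might infer that the study sets out to enrol dialysis patients. The text does not say so, and nothing shows that any will be enrolled. It only fails to keep them out, while the Patient screening section aims at a sample that resembles the wider cardiovascular population.
- **New dialysis is not simply ignored.** A reader might infer that it never counts. That is too strong: a subject whose creatinine rises by 0.3 mg/dL within 2 days and who then starts dialysis is counted. The gap is confined to treatment begun before such a rise is recorded, or after a slower or later one.
- **The main hypothesis is not at risk.** A reader might infer that false AKI events could produce the study's headline association. The stated hypothesis concerns cardiovascular and pulmonary injury, the primary outcome is VVFDs, and the plan specifies no test of AKI by PVD group. Nothing in the documents links dialysis with low PVD.
- **The size is easily overstated.** Dividing 1, 4 or 7 by 70 gives 1.4, 5.7 or 10 points. That treats every dialysis patient as otherwise a certain non-event. Against removal from the analysis set, the figures are 1.1, 4.3 and 7.5, and they still need the extreme allocation.
- **The undefined window and baseline affect every subject**, and a remedy tied to the same 2 days would inherit that gap.

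All of this stands as a limit on importance. The last part also shapes the fix, which has to define the baseline and window. None of it makes the two wrong classifications correct. Manual chart review would allow dialysis status to be identified at analysis, but a rule chosen then would be chosen with the results in view.

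**Conclusion.** The concern holds as a minor one. The stated AKI rule can count patients who are not at risk of new AKI, and it can miss a case treated with renal replacement before a qualifying rise is recorded. Only a secondary outcome is touched; VVFDs and the sample size are not.

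On the assumptions shown (1 to 7 dialysis patients, all in one PVD group of 70, all flagged, 25% AKI in the others), that group's AKI rate is overstated by about 1.1 to 7.5 percentage points. It is less if fewer are flagged, and roughly nothing net between groups if they split evenly. Missed cases would lower the observed rate by an unknown amount, so the net direction is also unknown.

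**What to change.** Leave eligibility as it is. In Outcome measures:

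1. Define the AKI analysis set as subjects not on renal replacement before surgery.
2. State that the 2-day window runs from surgery, with the preoperative creatinine as baseline.
3. Count renal replacement newly started within that window as AKI, whatever the creatinine.

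This concerns outcome classification only and directs no care. Renal replacement first started after the window would remain uncounted, in line with the 2-day definition.

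The cost is a short addition to the text and one baseline field (renal replacement before surgery). The Data sources section already provides for manual review of each record, so the field can also be filled for subjects already enrolled. The AKI denominator loses a few subjects. The change should be made before AKI is analysed.
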